### **Sample size calculation:**

In a recent cancer related intervention study by our team using oral dexamethasone (DM) [Yennurajalingam, S., S. Frisbee-Hume, et al. (2013)] compared to placebo was associated with improvement in FACIT-F subscale scores (mean, SD) of 9.6 (11) vs. 3.1 (9.7) ( $p=0.005$ ) at day 15.

However, we are investigating a different intervention (combination of fish oil and physical activity) and therefore we propose to detect a FACIT-F subscale change of 9.5 (standard deviation of 10) in Icosapent ethyl 2 gm orally daily plus PA group against 3 (standard deviation of 10) in placebo plus PA group, with 30 patients in each group, we have an 80% power to detect this difference (effect size 0.65) using a two-sided t-test with a significance level of 0.10. We will also collect information regarding the change in FACIT-F subscale score in 30 patients with placebo plus control physical activity, although not being compared with patients on fish oil and exercise. With a total of 30 patients in this group, we will have an 80% power to detect an effect size of 0.465 in the change in FACIT-F subscale score using a single group t-test with a 0.10 two-sided significance level. We will enter a total of 96 patients to allow for possible 5% dropout rate.

For the primary endpoint, we will compare the difference between the FACIT-F subscale score at baseline and at  $57\pm 5$  days, between patients who will receive Icosapent ethyl plus PA and placebo plus PA using t-test. Wilcoxon rank sum test may be considered if the distribution of the data is not normal. We will also compare the change of FACIT-F subscale scores among all three groups using ANOVA or Kruskal-Wallis test, whichever appropriate. At the end of the study, overall survival time in each group will be estimated using Kaplan-Meier method and may be compared among three treatment groups using log-rank test.

This study is considered feasible if patient is adherent to the study. Adherence will be calculated as the mean of the percentage of total prescribed strength training sessions, the percentage of total prescribed walking regimen minutes completed (PA), and the mean (across all patients) percentage of total prescribed pills taken (study medication). The adherence rate, as defined, is a continuous variable. At the end of the study, we will estimate the average adherence of prescribed strength, of total prescribed walking regimen minutes and of total prescribed pills taken separately using mean, standard deviation, median, and range. This study intervention of combination of Icosapent Ethyl and Physical activity will be considered feasible as evidenced by adherence rate is  $>/=75\%$  to daily combined therapy during the 8-week intervention. The adherence rate can also be compared among all three groups using Kruskal-Wallis test. We will estimate 95% confidence intervals for the proportion of patients completing the intervention, the adherence rate, and the proportion of patients with a satisfaction over time. With 30 patients in each arm, a 95% confidence interval for a proportion of 73% (22/30), for example, can be estimated as (54%, 88%).

Data of variables of interest will be summarized using standard descriptive statistics, such as mean, standard deviation, median, and range for continuous variables, frequency and proportion for categorical variables. Correlation will be assessed among continuous variables using Pearson or Spearman correlation coefficient, whichever is appropriate. Association between categorical variables will be examined by Chi-Squared test or Fisher's exact test when appropriate. Boxplot and histogram will be applied to demonstrate distribution of variables of interest.

Since FACIT-F scores will be obtained at 0, 15, 29, 43 and  $57\pm 5$  days, and other QOL variables and cytokine markers will also be obtained repeatedly over time, we will also evaluate the effect of treatment on the changes of these measured over time using repeated measure analysis in which intra-

patient correlation of the measures are accounted for. However due to the small scale and exploratory nature of the study, we will report p-value as is without adjusting for multiplicity.

To address issues related to missing data, we may perform multiple imputation analyses. If the data does not appear to be normally distributed, transformation may be employed to the data, or appropriate nonparametric methods will be used for data analysis.

Toxicity data will be summarized by treatment, grade and relationship using frequencies and cross-tabulation.

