**Plan for statistical analysis**

The primary objective is to study is to determine the difference between the FACIT-F subscale score at baseline and at Day  $57 \pm 5 \pm 5$  days, between patients who will receive either fish oil and exercise and placebo and exercise.

In a recent cancer related intervention study by our team using oral dexamethasone (DM) compared to placebo was associated with improvement in FACIT-F subscale scores (mean, SD) of 9.6 (11) vs. 3.1 (9.7) ( $p=0.005$ ) at day 15. However, we are investigating a different intervention (combination of fish oil and physical activity) and therefore we propose to detect a FACIT-F subscale change of 9.5 (standard deviation of 10) in Icosapent ethyl 2 gm orally daily plus physical activity group against 3 (standard deviation of 10) in placebo plus physical activity group, with 30 patients in each group, we have an 80% power to detect this difference (effect size 0.65) using a two-sided t-test with a significance level of 0.10. We will also collect information regarding the change in FACIT-F subscale score in 30 patients with placebo plus control physical activity, although not being compared with patients on fish oil and exercise. With a total of 30 patients in this group, we will have an 80% power to detect an effect size of 0.465 in the change in FACIT-F subscale score using a single group t-test with a 0.100 two-sided significance level. We will enter a total of 96 patients to allow for possible 5% dropout rate. For the primary endpoint, we will compare the difference between the FACIT-F subscale score at baseline and at  $57 \pm 5$  days, between patients who will receive Icosapent ethyl plus physical activity and placebo plus physical activity using t-test. Wilcoxon rank sum test may be considered if the distribution of the data is not normal. We will also compare the change of FACIT-F subscale scores among all three groups using ANOVA or Kruskal-Wallis test, whichever appropriate. At the end of the study, overall survival time in each group will be estimated using Kaplan-Meier method and may be compared among three treatment groups using log-rank test.

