Adherence will be calculated as the % of total prescribed strength training sessions, the % of total prescribed walking regimen minutes completed (physical activity), and the percentage of total prescribed pills taken (study medication). The adherence rate, as defined, is a continuous variable. At the end of the study, we will estimate the average adherence of prescribed strength, of total prescribed walking regimen minutes and of total prescribed pills taken separately using mean, standard deviation, median, and range. The adherence rate can also be compared among all three groups using Kruskal-Wallis test. We will estimate 95% confidence intervals for the proportion of patients completing the intervention, the adherence rate, and the proportion of patients with a satisfaction over time. With 30 patients in each arm, a 95% confidence interval for a proportion of 73% (22/30), for example, can be estimated as (54%, 88%).

Data of variables of interest will be summarized using standard descriptive statistics, such as mean, standard deviation, median, and range for continuous variables, frequency and proportion for categorical variables. Correlation will be assessed among continuous variables using Pearson or Spearman correlation coefficient, whichever is appropriate. Association between categorical variables will be examined by Chi-Squared test or Fisher's exact test when appropriate. Boxplot and histogram will be applied to demonstrate distribution of variables of interest.

Since FACIT-F scores will be obtained at 0, 15, 29, 43 and  $57\pm5$  days, and other QOL variables and cytokine markers will also be obtained repeatedly over time, we will also evaluate the effect of treatment on the changes of these measured over time using repeated measure analysis in which intra-patient correlation of the measures are accounted for. However due to the small scale and exploratory nature of the study, we will report p-value as is without adjusting for multiplicity.

To address issues related to missing data, we may perform multiple imputation analyses. If the data does not appear to be normally distributed, transformation may be employed to the data, or appropriate nonparametric methods will be used for data analysis. Toxicity data will be summarized by treatment, grade and relationship using frequencies and cross-tabulation.

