## 7.0. Outcome Measures/Planned Assessments

### 7.1. Timing of assessments

ASSESSMENTS	Table 4. Study assessments for Icosapent ethyl/Placebo.									
	Baseline	Day 8* (± 3)	Day 15* (± 3)	Day 21* (± 3)	Day 29 (± 3)	Day 36* (± 5)	Day 43* (± 5)	Day 50* (± 5)	Day 57 (± 5)	1 month post open label phase † (± 5)
History/ Physical exam	X				X				X	
Zubrod score	X									X
Medication review	X	X	X	X	X	X	X	X	X	X
FACIT-F subscale, FACT-G, MFSI-SF, PROMIS-Fatigue, HADS, PSQI	X		X		X		X		X	X
ESAS	X	X	X	X	X	X	X	X	X	X
Physical Performance Tests (30 second chair stand test, six-minute walk test, accelerometer, Godin leisure-time PA questionnaire)	X				X				X	X
Body composition Body Mass Index (Bio Impedance), Resting energy expenditure using indirect calorimetry§	X				X				X	X
Cytokines (CRP, Serum IL-1b, TNF-α, IL-6; Intracellular cytokines IL-6 R; TNF R, IL- 1R, IL-10)	X				X				X	
Electrolytes liver function tests, PT/INR**, CBC**	X		X		X		X		X	X
Toxicity evaluation		X	X	X	X	X	X	X	X	X
Global Symptom Evaluation									X	

† patients in control arm and the intervention arm will have an option of treatment in drug or placebo +exercise arms

\*Assessment by phone or in person

\*\* PT/INR at baseline only unless patient is being treated with prophylactic anticoagulants. CBC at baseline only unless more frequently testing is clinically indicated.

-Assessments are performed by the Palliative Care team and complements the standard of care provided by the GI medical oncologists

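### The primary t-test on Day 57 FACIT-F change is valid and has its stated 80% power, but a pre-specified ANCOVA on baseline FACIT-F could be more precise at almost no cost

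*Combined protocol and SAP*

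**What the plan says.** The primary analysis appears twice, in the same form. Section 8, under the sample size heading, takes the change in FACIT-F over the eight weeks to Day 57 as the primary endpoint and compares it "between patients who will receive Icosapent ethyl plus PA and placebo plus PA using t-test". The synopsis, in its plan for statistical analysis, has the comparison "between patients who will receive Icosapent ethyl plus physical activity and placebo plus physical activity using t-test". A Wilcoxon rank sum test is the possible fallback for non-normal data. No covariate is named in either place.

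The sample size rests on the same test. For a mean change of 9.5 against 3, SD 10 in each arm and 30 patients per arm, the plan states "we have an 80% power to detect this difference (effect size 0.65) using a two-sided t-test with a significance level of 0.10".

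Table 4 in Section 7.1 lists "FACIT-F subscale, FACT-G, MFSI-SF, PROMIS-Fatigue, HADS, PSQI" at baseline and Day 57, among other visits, so the baseline score will be available. Section 8 adds a longitudinal analysis: "we will also evaluate the effect of treatment on the changes of these measured over time using repeated measure analysis". Both the synopsis and Section 8 say that this model allows for correlation within a patient. That analysis is additional to the primary test, and neither place says how the Day 0 score enters the model.

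**The concern.** A t-test on change does use the baseline score, but with a slope fixed at 1. The slope that minimises the residual variance is rho × SD(Day 57)/SD(baseline), where rho is the within-arm correlation between the two visits. If that value is well away from 1, the change score carries more residual variance than a model that estimates the slope, and the effect estimate is less precise than the same data allow.

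Chance imbalance is a related issue with about 30 patients per arm. Assume a baseline SD of 10. The difference in baseline means between arms then has a standard error of 10 × √(2/30) = 2.58 points. If the true slope were 0.5 (also an assumption), a one-standard-error imbalance would move the change-score estimate by 0.5 × 2.58 ≈ 1.3 points, a fifth of the 6.5-point target. This averages to zero over repeated trials, so it is not bias. It does affect the one estimate that a phase II trial carries forward.

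**Working it through.** **Inputs from Section 8.** Difference 9.5 − 3 = 6.5 points; SD of change 10; 30 evaluable patients per arm; two-sided alpha 0.10.

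**Inputs not in the documents.** The correlation rho, and k = SD(Day 57)/SD(baseline). Both are assumptions and are shown as ranges.

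**1. The plan's own figure.** SE = 10 × √(2/30) = 2.582, with 58 degrees of freedom and critical value 1.672. The noncentrality is 6.5/2.582 = 2.517, which gives exact power of 80.04%. The 90% interval half-width is 1.672 × 2.582 = 4.32 points. The stated 80% reproduces.

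**2. ANCOVA on arm and baseline.** The SD of change is held at 10, as the plan assumes, so that:

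- SD(baseline) = 10/√(1 + k² − 2·rho·k)
- residual SD = k × SD(baseline) × √(1 − rho²)
- SE = residual SD × √[(2/30) × (1 + 1/56)], with 57 degrees of freedom. The factor 1 + 1/56 is the average penalty for estimating the slope.

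For k = 1.0 and rho = 0.5, SD(baseline) = 10, residual SD = 8.66 and SE = 8.66 × 0.2605 = 2.256. Power is 88.5% and the half-width is 1.672 × 2.256 = 3.77.

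| k | rho | Slope (k × rho) | Residual SD | Power | Half-width |
|---|---|---|---|---|---|
| 0.8 | 0.3 | 0.24 | 7.09 | 96.7% | 3.09 |
| 0.8 | 0.5 | 0.40 | 7.56 | 94.7% | 3.29 |
| 0.8 | 0.7 | 0.56 | 7.92 | 92.9% | 3.45 |
| 1.0 | 0.3 | 0.30 | 8.06 | 92.1% | 3.51 |
| 1.0 | 0.5 | 0.50 | 8.66 | 88.5% | 3.77 |
| 1.0 | 0.7 | 0.70 | 9.22 | 84.8% | 4.02 |
| 1.2 | 0.3 | 0.36 | 8.73 | 88.1% | 3.80 |
| 1.2 | 0.5 | 0.60 | 9.33 | 84.1% | 4.06 |
| 1.2 | 0.7 | 0.84 | 9.83 | 80.6% | 4.28 |
| 1.2 | 0.8 | 0.96 | 9.98 | 79.5% | 4.35 |
| 1.3 | 0.3 | 0.39 | 8.97 | 86.5% | 3.91 |
| 1.3 | 0.5 | 0.65 | 9.55 | 82.6% | 4.16 |
| 1.3 | 0.7 | 0.91 | 9.95 | 79.7% | 4.34 |
| 1.3 | 0.8 | 1.04 | 9.99 | 79.5% | 4.35 |
| 1.4 | 0.6 | 0.84 | 9.90 | 80.1% | 4.31 |
| 1.4 | 0.7 | 0.98 | 10.00 | 79.4% | 4.35 |
| Planned t-test | – | fixed at 1 | 10.00 | 80.0% | 4.32 |

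A correlation of 0.9 with k of 0.8 or 1.0 is left out of the table. With the SD of change at 10 it implies a baseline SD of 22.4. If the 13 items scored 0 to 4 are summed to a 0-52 scale, that is not credible.

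**3. Worst case.** If the true slope is exactly 1, the residual SD stays at 10. ANCOVA power is then 79.4% and the half-width 4.36, a loss of about 0.6 percentage points of power and 0.04 points of width.

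**4. Break-even.** ANCOVA matches the t-test's power at a residual SD of 9.91, which is 98.2% of the change-score variance. The change variance equals the residual variance plus (1 − slope)² × Var(baseline). ANCOVA therefore gains power when |1 − slope| × SD(baseline) exceeds 10 × √(1 − 0.982) ≈ 1.34 points. For a baseline SD of 8, 10 or 13, the slope must differ from 1 by more than 0.17, 0.13 or 0.10.

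**5. Simulation (40,000 trials per cell).** The t-test's power was 0.798 to 0.805 throughout, and ANCOVA's agreed closely with the calculated values. Type I error was 0.096 to 0.103 for both tests at nominal 0.10. Both estimators averaged 6.48 to 6.52 at a true difference of 6.5, so neither is biased.

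**The case against.** The best case for leaving the plan alone is that nothing in it is wrong. The objective, the sample size and the primary test all use the change score consistently, the type I error is right and the declared power is met. That stands, and it is why this is a recommendation and not a required correction.

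The benefit also rests on quantities that the documents do not give, and the range shown includes no gain. Four of the 16 ANCOVA rows fall slightly below the t-test, and two more are within 0.6 percentage points above it. This stands too. The largest gain, about 17 percentage points (96.7% against 80.0%), needs Day 57 scores to be less variable than baseline scores together with a low correlation. Entry on a fatigue criterion might narrow the baseline spread and push k above 1, where gains are smaller. The 17-point figure should not be read as expected.

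The planned repeated-measures analysis may already use the Day 0 score. It is secondary, though, and does not say how baseline is handled, so it does not settle the primary estimate.

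Finally, making ANCOVA primary leaves the fallback for non-normal data to be restated. That is fair, and one clause deals with it.

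**Conclusion.** The point holds as an efficiency improvement of uncertain size, with medium confidence. The primary analysis has no baseline adjustment, yet it is valid and has its stated power of 80.0% with 30 evaluable patients per arm.

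With equal SDs at the two visits and rho of 0.5 to 0.7, ANCOVA would add about 5 to 8.5 percentage points of power and take 0.30 to 0.55 points off the half-width. The gain shrinks to nothing as the slope approaches 1, and the most that can be lost is about 0.6 percentage points. The balance therefore favours adjustment even though the gain cannot be fixed in advance.

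These figures assume an SD of change of 10, a common linear baseline slope in both arms and complete Day 57 data. They do not address bias from missing Day 57 scores.

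**What to change.** Replace the primary-analysis sentence in Section 8 and in the synopsis. The primary analysis becomes a linear model of Day 57 FACIT-F (or its change) on treatment arm and baseline FACIT-F in the two physical-activity arms, tested at two-sided alpha 0.10 and reported with a 90% confidence interval. Keep the unadjusted t-test and the Wilcoxon rank sum test as sensitivity analyses, and say that neither replaces the primary model after the data are seen. Fix this wording before outcome data are examined; otherwise the covariate becomes a choice between results.

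The cost is the wording and one degree of freedom (57 instead of 58), with the worst-case loss given above. Sample size, visits and data collection stay as they are.

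### The primary t-test has no binding rule for missing Day 57 scores and leaves out the interim FACIT-F visits, so it can be biased in either direction if fatigue-related loss differs between the two compared arms

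*Combined protocol and SAP*

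**What the plan says.** All of the following is in the protocol, section 8, under the sample size calculation; the statistical plan in the synopsis repeats it.

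- **Primary test.** The change from baseline to Day 57 is compared "between patients who will receive Icosapent ethyl plus PA and placebo plus PA using t-test". The fallback, "Wilcoxon rank sum test may be considered if the distribution of the data is not normal", uses the same single change score.
- **Interim scores.** The repeated-measures paragraph opens "Since FACIT-F scores will be obtained at 0, 15, 29, 43 and" and goes on to Day 57. It commits to an analysis that allows for within-patient correlation, but as something done in addition to the primary test.
- **Missing data.** The only statement is "To address issues related to missing data, we may perform multiple imputation analyses". It gives no imputation model and no trigger, and it does not say whether imputation applies to the primary test.
- **Loss allowed for.** "We will enter a total of 96 patients to allow for possible 5% dropout rate". Section 5.2.3 rules out replacement of withdrawn patients.

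Section 7.3 defines a safety population. No efficacy analysis population is defined, and nothing says which result prevails if the t-test and the repeated-measures analysis disagree.

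**The concern.** A two-sample test on a change score can use only patients who have both scores, unless a rule says otherwise, and here the one candidate rule is optional. The patients are fatigued and have advanced cancer. Section 5.2.1 lists death, intercurrent illness, decline in performance status and non-compliance among the reasons for leaving the trial, so a link between loss and worsening fatigue is plausible.

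Table 4 marks Days 15 and 43 as possible by telephone but does not mark Day 57. A patient may therefore have a Day 43 score and no Day 57 score, and the primary test would discard the Day 43 information. Section 7.2.6 does mention questionnaires completed by telephone, so this is only suggestive.

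At stake are the size of the estimated drug effect, the error rate of the 0.10 test, and a choice of estimator that stays open until the data are seen.

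**Working it through.** **1. Reproduce the design.** The inputs from section 8 are changes of 9.5 and 3, SD 10 in both arms, 30 per arm and two-sided alpha 0.10.

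- Effect size: (9.5 - 3)/10 = 0.65.
- Noncentrality: 0.65 × √(30/2) = 2.52 on 58 degrees of freedom. Power is 80.0%, as stated.
- Enrolment: 30/0.95 = 31.6, so 32 per arm, and 3 × 32 = 96, as stated.

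**2. Power if loss exceeds 5%** (loss rates assumed, 32 enrolled per arm, loss unrelated to outcome):

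| Loss | Evaluable per arm | Power of t-test |
|---|---|---|
| 5% | 30 | 80.0% |
| 10% | 29 | 78.8% |
| 15% | 27 | 76.2% |
| 20% | 26 | 74.8% |
| 30% | 22 | 68.3% |

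**3. When the completer contrast is biased.** In one arm, let p be the share lost and gap the completers' mean change minus the mean change of those lost. The completer mean exceeds the full-arm mean by p × gap. For the difference between arms, with T for icosapent ethyl + PA and C for placebo + PA:

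bias = p_T × gap_T - p_C × gap_C

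- Equal shares and gaps, 20% each, gap 10: 2.0 - 2.0 = 0.
- 10% against 20%, gap 10: 1.0 - 2.0 = -1.0 point.
- 10% against 30%, gap 10: 1.0 - 3.0 = -2.0 points.

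So losing sicker patients is not enough. The amount of loss, or its link to outcome, must differ between arms, and the sign follows the arm where p × gap is larger.

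**4. Size by simulation.** There are five visits and 32 patients per arm, with change SD 10, true difference 6.5 and an assumed visit correlation of 0.7. Patients leave for good, with a probability that depends on their last observed change from baseline. Loss in the other arm is unrelated to fatigue unless stated. All loss rates are assumptions.

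| Scenario | Completer difference | Bias | All-visit likelihood estimate |
|---|---|---|---|
| Fatigue-driven loss, icosapent ethyl arm only | 7.3 | 7.3 - 6.5 = +0.8 | about 6.5 |
| Fatigue-driven loss, placebo + PA arm only | 5.4 | 5.4 - 6.5 = -1.1 | about 6.5 |
| Same mechanism in both arms | 6.2 | 6.2 - 6.5 = -0.3 | about 6.5 |
| About 5% loss | close to 6.5 | almost none | close to 6.5 |

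Fatigue-driven loss in the first two rows is about 20-27%. With no true effect, one-arm loss of this kind gives two-sided rejection of about 11-12% against 10%. The same mechanism in both arms gives no inflation.

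**5. Sensitivity to the assumptions.**

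- Separate runs with other correlation structures gave 6.42-6.55 at about 5% loss, and 6.1-6.5 at about 20% loss with the same mechanism in both arms. The low end of the second range (bias about 0.4) arose when loss depended on the unobserved score.
- A steeper dependence of loss on fatigue gave 8.7 (icosapent ethyl arm only), 4.3 (placebo + PA arm only) and 5.9 (both arms), against a true 6.5. The likelihood estimate in the two one-arm cases was 6.6.
- If loss depends on the raw last score instead of the change, the bias is smaller and of opposite sign.
- If loss depends on the unobserved score, the likelihood estimate recovers only part. With about 9% against 28% lost, the completer difference was 5.3 and the likelihood estimate 5.9.

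**The case against.** The best case for the plan has four parts.

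- **Bias is not shown.** A reader might infer that losing sicker patients biases the primary contrast as such. The documents do not support that. They give no loss by arm, the two compared arms take capsules of identical appearance and follow the same exercise programme, and a common mechanism largely cancels. This stands: the contrast can be biased, but nothing shows that it will be.
- **The interim scores are not ignored.** A reader might also infer that the plan wastes them. It does not, because it commits to a repeated-measures analysis of every FACIT-F visit. This stands for the plan as a whole but not for the primary test, and no rule covers a disagreement between the two.
- **The error inflation is modest.** Counting only false positives that favour the drug makes it look like a doubling. In one run, 10.7% of trials rejected in favour of the drug and 2.0% against it. The test is two-sided at 0.10, so the fair comparison is 10.7% + 2.0% = 12.7% against 10%. This stands.
- **Loss may be low.** Eligibility requires Zubrod 1 or less and a life expectancy of at least 4 months, and several assessments may be done by telephone. At the planned 5% the two methods agree. This also stands; the 20-27% is an assumption.

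A mandatory, defined imputation for the t-test would close the same gap, so the repeated-measures model is not the only remedy. None of this supplies the missing rule: imputation remains optional and the efficacy population undefined.

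**Conclusion.** The point holds in a conditional form. As written, the primary test leaves out patients without a Day 57 score, makes no use of their interim scores, and has no binding missing-data rule.

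If 20-27% loss depends on change from baseline in one arm only, with visit correlation 0.7, the bias is about 1 point on a 6.5-point target (+0.8 or -1.1) and the two-sided error is about 11-12% against 10%. With the same mechanism in both arms, or at the planned 5% loss, the bias in these settings is at most about 0.3 points. These sizes rest on assumed loss rates, correlation and mechanism, and a different mechanism changes both size and sign. They show what the plan leaves unprotected and do not predict the result. The change is worth making because it is cheap and the better analysis is already planned.

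**What to change.** In section 8 and in the synopsis:

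1. Name as primary the Day 57 contrast, icosapent ethyl + PA minus placebo + PA, from the repeated-measures model already planned, with visit-by-arm means and unstructured covariance, tested at two-sided 0.10.
2. Define its population as all randomised patients with a baseline and at least one later FACIT-F score.
3. Keep the completer t-test as a supportive analysis.
4. Replace the optional imputation with a specified not-at-random sensitivity analysis that covers deaths and patients with no post-baseline score.

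The cost is plan wording and slightly more analysis work, with no new visits, data or patients. The limitation to state in the plan is that the model is unbiased only when loss depends on observed scores; otherwise it corrects only part of the bias, which is why item 4 is needed.
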